3. Comparable postoperative Oswestry Disability Index (ODI) score (0-no disability, to 100-maximum disability possible), two weeks, 6 weeks, 3 months, 6 months, and 1 year postoperatively
4. Comparable fusion rates, evaluated via CT scan 1 year postoperatively

Study Benefits to Virtua

Virtua could stand to gain some significant cost savings if the more cost-effective Vivigen is shown to be a clinically equivalent bone graft option that can replace the more expensive rhBMP-2.

Study Methodology

Patients who meet all of the following inclusion criteria may be eligible to participate in the study if:

1. Age 18 or older;
2. Diagnosed with lumbar degenerative/isthmic spondylolisthesis, degenerative disc disease with axial low back pain and neurologic symptoms, failed conservative treatment and eligible for a single level lumbar instrumented fusion;
3. Willing to provide informed consent, participate in study, and comply with study protocol.

Patients who meet any of the following criteria may not be eligible to participate:

1. Pregnant or contemplating pregnancy prior to surgery;
2. Serious spinal conditions (e.g. spinal cord compression, cauda equina syndrome, spinal infection, spinal tumor, spinal fracture, inflammatory or systemic spinal arthritis);
3. Surgery involving more than 2 vertebral levels;
4. Worker's compensation or personal injury related to lumbar spine (treatment outcomes may be affected by patient's personal interests; could also run into potential issues with reimbursement).
5. Lactating women
6. Patients who have a known or suspected allergy to Gentamicin Sulfate, Meropenem, Vancomycin, Dimethyl Sulfoxide (DMSO), and Human Serum Albumin
7. Immune compromised patients

During the preoperative office visit, the surgeon will inform patients that appear to meet study eligibility criteria, about the study, and discuss the differences between the two bone graft options, including their potential risks and benefits. The surgeon will make clear to the patient that consenting to be a part of the study means that the patient has agreed to be randomly assigned to one of the two bone graft groups.

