Patients who are deemed eligible to participate in the study and are willing to participate will be asked by a trained study physician assistant (PA) to complete the research informed consent. This document will be summarized verbally by the PA and potential participants will be given the opportunity to ask questions about the protocol or their involvement prior to providing consent. Those who agree to

participate and provide research informed consent will be enrolled in the study, and given a copy of the research informed consent document. The patient's informed consent would be added to the patient's chart.

A computer generated randomization scheme will be employed and the randomization outcomes will be sealed in envelopes. On the day of surgery, in the operating room, the circulating nurse will pick an envelope from the randomized stack, unseal the envelope, and based on the outcome (even or odd), assign the patient to one of the two bone graft groups. While the study intervention group (even) will receive 5cc Vivigen and local autograft, the control group (odd) will receive small kit rhBMP-2 with local autograft. Anesthesiologists will use their usual pre-operative and intra-operative techniques for all study participants.

The surgical team, including the surgeons, will be blinded to the treatment options until decompression/instrumentation have been completed. The patients and all staff, including hospital nursing staff, case management, and physical therapists, will be blinded as to which bone graft treatment the patient received.

The primary outcome in this study will be the mean Oswestry Disability Index (ODI) score. The ODI is one of the most commonly utilized condition-specific measures of disability used in the management of spinal disorders [9]. The ODI Version 2.0 is what the Virtua Memorial Spine Center currently uses to examine patient disability preoperatively, as well as two weeks, 6 weeks, 3 months, 6 months, and 1 year postoperatively. The ODI has 10 sections of six statements with the first statement corresponding to a score of 0 indicating no disability and the last statement corresponding to a score of 5 indicating maximum possible disability. The final score which is calculated as: $[\text{total score}/(5 \times \text{number of questions answered})] \times 100\%$, could range from 0% to 100% [9].

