Adopting a standard deviation of 10, which is one of the most commonly used standard deviations in ODI studies [9], and looking to detect a mean difference of 8 in ODI scores to indicate superiority of one bone graft option over the other, it is estimated that for a statistical power of 80% and significance level of 0.05, a minimum of 26 participants will be required in each study group for a total of 52 study participants. To minimize the possibility of dropouts or incomplete data impacting the analysis, a minimum of 30 participants will be enrolled in each study group, for a total of 60 study participants.

Secondary outcome measures in this study include the mean scores from the 36-Item Short Form Survey Instrument (SF-36) [10]; the mean leg/back pain scores from the numeric rating scale of 0-no pain, to 10-worst pain possible; mean LOS; incidence of ORAEs, and fusion rates examined via CT scan 1 year postoperatively by an independent radiologist.

Means will be compared between the two study groups using one-tailed 2-sample t tests, proportions will be compared using chi-square tests, and logistic regression will be used to analyze for confounding effects. All statistical analyses will be conducted in Minitab 16 Statistical Software.

Protection of Human Subjects

Throughout the study, the principal investigators (Virtua Memorial spine surgeons and PAs), will be the only ones with access to the data collection database. Following the completion of the study, all personal health information collected, including name, gender, age, significant medical comorbidities, and postoperative complications, will be de-identified as soon as possible prior to data analysis and any subsequent publications or research submissions. Patient would be told participation is purely voluntary with no monetary reimbursement and minimal risk of being assigned to one of the two pain management groups.

References

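### The primary ODI comparison is an unadjusted t test, the only adjustment model named cannot adjust a mean, and preoperative ODI is left unused, at a cost in precision

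*Combined protocol and SAP*

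**What the plan says.** The primary-outcome paragraph of Study Methodology states: "The primary outcome in this study will be the mean Oswestry Disability Index (ODI) score". It adds that the centre's spine service uses the index now, before surgery and at five later visits: "currently uses to examine patient disability preoperatively, as well as two weeks, 6 weeks, 3 months, 6 months, and 1 year postoperatively". Item 3 of the hypotheses concerns the score after surgery, not the change from baseline: "Comparable postoperative Oswestry Disability Index (ODI) score".

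The analysis is given in one sentence at the end of Study Methodology. For continuous outcomes: "Means will be compared between the two study groups using one-tailed 2-sample t tests". Proportions get chi-square tests. For adjustment: "logistic regression will be used to analyze for confounding effects", with no outcome and no covariates named. No linear model, analysis of covariance (ANCOVA), mixed model or change score appears anywhere in the document.

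**The concern.** The plan intends to look at confounding but names a model for binary outcomes only. That model could serve fusion and adverse events. It cannot serve mean ODI, SF-36, pain or length of stay, so no adjusted analysis of the primary outcome is described. Preoperative ODI is the obvious covariate. It is mentioned only as current clinic practice; it is not expressly required of trial patients and it enters no analysis.

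This matters more than usual here because the hypothesis is comparability. A claim that the two grafts perform alike is only as good as the interval around the ODI difference is narrow. The trial is also small, and no stratification on baseline is described, so a chance difference in preoperative ODI would pass partly into the result uncorrected.

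**Working it through.** **Inputs from the sample-size paragraph of Study Methodology:** SD 10, difference 8, power 80%, significance level 0.05, 26 per group needed, 30 per group enrolled.

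**Assumptions:** r, the correlation between preoperative and postoperative ODI, is not in the documents, so 0.3, 0.5 and 0.6 are shown, with lower values in step 3. Step 4 also assumes a preoperative SD of 10.

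**1. The plan's own figure.** For an unadjusted two-sample t test with 26 per group, the standard error is 10 × √(2/26) = 2.77. The noncentrality is 8/2.77 = 2.88 on 50 degrees of freedom, and two-sided power is 80.7%. Solving for 80% gives 25.5, so 26 per group: the plan's figure is reproduced. A one-sided calculation gives 21 and does not reproduce it. The sample size therefore takes no credit for baseline.

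**2. With baseline adjustment.** The residual SD is 10 × √(1 − r²), which is 9.54, 8.66 and 8.00 for the three values of r. The degrees of freedom are 2n − 3 instead of 2n − 2. The half-width of the 95% interval is t(0.975) × residual SD × √(2/n).

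| | Unadjusted | r = 0.3 | r = 0.5 | r = 0.6 |
|---|---|---|---|---|
| Two-sided power, 26 per group | 80.7% | 84.2% | 90.4% | 94.2% |
| Two-sided power, 30 per group | 86.1% | 89.1% | 94.0% | 96.8% |
| One-tailed power, 26 per group | 88.5% | 90.9% | 94.9% | 97.2% |
| One-tailed power, 30 per group | 92.2% | 94.1% | 97.1% | 98.5% |
| 95% CI half-width, 26 per group (points) | 5.57 | 5.32 | 4.83 | 4.46 |
| 95% CI half-width, 30 per group (points) | 5.17 | 4.93 | 4.48 | 4.14 |

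The one-tailed rows are shown because that is the test the plan names.

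**3. Check by simulation.** The formula ignores the small extra variance that arises when the groups differ by chance at baseline. Simulating ANCOVA with a random baseline (40,000 replicates, 26 per group, two-sided) gives power of 83.5%, 89.7% and 93.8% at r = 0.3, 0.5 and 0.6, which is 0.4 to 0.7 points below the formula. At low correlation, the same calculation gives 79.9% at r = 0, 80.3% at r = 0.1 and 81.5% at r = 0.2, against 80.7% unadjusted.

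**4. Chance imbalance.** With a preoperative SD of 10, the standard error of the baseline difference is 2.77 at 26 per group and 2.58 at 30. The chance that it exceeds 4 points in either direction is 14.9% and 12.1%. With equal SDs before and after surgery, the unadjusted difference shifts by about r times the imbalance: 4 × 0.3 = 1.2, 4 × 0.5 = 2.0 and 4 × 0.6 = 2.4 points, against a target difference of 8.

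**The case against.** The strongest reply is that this is a preference for efficiency, not a defect. The t test is unbiased under randomisation, its standard error already allows for chance imbalance, and the planned number meets its 80% target without adjustment. With 30 per group and the one-tailed test, power is already 92.2%, and r = 0.3 lifts it only to 94.1%. All of that is correct, and it is why the point concerns precision and not validity.

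The size of the gain does rest on an r that the documents do not supply, and adjustment gains almost nothing at r of 0.2 or less. The downside is just as limited: under one power point at r = 0. The formula figures are slightly favourable, by less than one power point.

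It can also be said that listing the preoperative measurement beside the later visits implies it will be collected, and that the logistic sentence may be meant only for the binary outcomes. On those readings the baseline would be available, but it would still be unused, and mean ODI would still have no adjusted analysis.

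Finally, adjustment does not settle what comparable means: the plan gives no margin, so a narrower interval cannot be shown to change a stated decision. That is a separate gap. It does not remove the value of a more precise estimate.

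**Conclusion.** The concern holds. The model named for confounding cannot adjust the primary outcome, and a prognostic measurement the clinic already takes is not used. At 26 per group the two-sided gain is about 3 power points at r = 0.3 (83.5% simulated, 84.2% by formula, against 80.7%), about 9 to 10 points at r = 0.5 and about 13 at r = 0.6. The half-width narrows by about 0.25, 0.7 and 1.1 points respectively. For the one-tailed test at 30 per group the power gain is smaller, about 2 to 6 points. These figures rest on the plan's SD of 10 and difference of 8, and on the assumed r. The textual gap is certain; its cost is not. It should be corrected, but it does not make the planned comparison invalid.

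**What to change.** - Make the primary analysis a linear model (ANCOVA) of postoperative ODI on treatment group and preoperative ODI, and report the adjusted difference with its 95% confidence interval.
- Fit it at one named visit. The 1-year visit, when CT fusion is also read, is one candidate; the other four would then be secondary.
- Require a preoperative ODI from every randomised patient, completed before the envelope is opened.
- Use the same form of model for SF-36 and pain where a preoperative value exists.
- Confine logistic regression to the binary outcomes (fusion and adverse events).

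The cost is one degree of freedom, one form per patient that the clinic already uses, the choice of a primary visit, and a wording change made before outcome data are seen. No extra patients are needed.

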IRB Application for Population Health and Quality Research Study

Title of Study: rhBMP-2 versus Vivigen, a novel cellular allograft, in lumbar fusion procedures: a prospective randomized controlled study

Background and Statement of Context

Instrumented lumbar fusion procedures with bone graft are one of the most common procedures performed today. There are numerous bone graft options, including iliac crest bone graft, local autograft, allograft, extenders, and rhBMP [1]. Several studies have demonstrated the efficacy and complications associated with these bone graft options [2-6]. Iliac crest autograft, long considered the gold standard of bone graft, is associated with donor site morbidity, longer operative times, and limited availability [7]. Recombinant human bone morphogenetic protein-2 (Infuse) has revolutionized lumbar fusion surgery. Initially approved for a single level ALIF, Infuse has been utilized in many off-label applications. Further studies of Infuse demonstrated multiple adverse effects, such as osteolysis, ectopic bone formation, retrograde ejaculation, and potentially carcinogenesis [8]. The premium cost and adverse effects of Infuse has led researchers to develop other options. A novel bone graft option is the cellular allograft, a cryopreserved mixture of viable bone cells, demineralized bone matrix, and cancellous bone chips. This product is purported to be osteogenic, osteoinductive, and osteoconductive. There is a paucity of literature evaluating these cellular allograft bone graft options in lumbar spine surgery. This study is aimed at comparing the overall efficacy (clinical and radiographic) of Vivigen, a novel cellular allograft product, and rhBMP-2 when utilized in lumbar fusion procedures.

Study Questions/Objectives and Hypothesis

The purpose of this study is to compare the overall efficacy (clinical outcome and radiographic fusion) of Vivigen (cellular allograft product) and rhBMP-2 in patients who undergo a single level lumbar instrumented fusion. Specifically, when compared to their control group counterparts treated to rhBMP-2, we hypothesize that the intervention group administered Vivigen would, following surgery, experience:

1. Comparable mean postoperative leg/back pain score, where the pain scores are obtained using the numeric rating scale of 0-no pain, to 10-worst pain possible
2. Comparable inpatient length of stay (LOS)

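### The Protection of Human Subjects section has patients told of minimal risk from assignment to pain management groups, which misnames the two bone graft arms and is not reconciled with the risks set out in the Background

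*Combined protocol and SAP*

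**What the plan says.** The last sentence of Protection of Human Subjects sets out what patients will hear. It opens: "Patient would be told participation is purely voluntary with no monetary reimbursement". It then adds a statement about risk: "minimal risk of being assigned to one of the two pain management groups".

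Study Methodology describes the randomised choice differently. The surgeon is to explain what enrolment commits the patient to: "consenting to be a part of the study means that the patient has agreed to be randomly assigned to one of the two bone graft" […], so the allocation is defined by graft. The arms are then specified: the intervention group "will receive 5cc Vivigen and local autograft, the control group (odd) will receive small kit rhBMP-2 with local autograft". Before consent, the surgeon is also to "discuss the differences between the two bone graft options, including their potential risks and benefits". A PA then summarises the written consent document and invites questions, and the patient keeps a copy.

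On risk, the Background reports that studies of rhBMP-2 showed "multiple adverse effects, such as osteolysis, ectopic bone formation, retrograde ejaculation, and potentially carcinogenesis". On the other product class it says: "There is a paucity of literature evaluating these cellular allograft bone graft options in lumbar spine surgery".

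**The concern.** The sentence is not loose background prose. It prescribes what patients are told, and it has two faults.

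- **It names the wrong interventions.** A patient told only this would think that the trial compares ways of managing pain, when it compares materials placed at a fusion site.
- **It calls the risk minimal without saying which risk is meant.** The same document names specific harms for one arm and acknowledges thin evidence for the other.

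What is at stake is the accuracy and consistency of what participants are told. An IRB reading the application would also find two descriptions of the arms, and a risk statement that the Background does not support as it stands.

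**Working it through.** No figure in the plan bears on this point, so the check is a comparison of texts.

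**1. Is pain management randomised anywhere?**

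| Place | What it gives as the groups or treatment |
|---|---|
| Title, and objectives | Vivigen compared with rhBMP-2 |
| Study Methodology, recruitment | Two bone graft groups |
| Study Methodology, randomisation | 5cc Vivigen or small kit rhBMP-2, each with local autograft |
| Study Methodology, anaesthesia | "Anesthesiologists will use their usual pre-operative and intra-operative techniques for all study participants" |
| Study Methodology, secondary outcomes | Leg/back pain score, as a measured outcome |
| Protection of Human Subjects | Two pain management groups |

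The last row stands alone. Anaesthetic technique, the closest the methodology comes to pain management, is left to usual practice for everyone. Pain itself is only an outcome. The label is therefore wrong on any reading.

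**2. What can minimal risk mean here?** Three readings are possible.

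- *The chance of being assigned is small.* This is the literal grammar, but it cannot be intended, because every enrolled patient is assigned to one group or the other.
- *The treatment received carries little risk.* The Background names four adverse effects of rhBMP-2, one of them qualified as potential, and describes a sparse literature on cellular allografts. The protocol does not reconcile this reading with that text.
- *Being allocated by chance adds little risk for someone already having a fusion.* This is coherent, but the sentence does not say it and the protocol does not argue for it.

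The second and third readings tell a patient different things, and the text does not choose between them.

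**3. How many patients does it concern?** The plan enrols at least 30 per group, so at least 30 + 30 = 60 in total. The sentence as written applies to all of them. This counts patients covered by the instruction, not patients shown to have been misinformed. The documents give no adverse event rates for either graft, so the size of the risk cannot be calculated.

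**The case against.** The strongest defence is that the rest of the consent process is sound. The surgeon names the bone graft groups correctly and discusses the risks and benefits of both. A written document, a verbal summary and time for questions follow. The wrong label may simply be a slip. In addition, the risk phrase is attached to being assigned, so it may refer only to the added risk of random allocation among patients who are having a single level fusion anyway. A list of types of harm, without rates, does not settle how large that added risk is.

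Most of this stands, and it limits the point. It does not remove it: correct text elsewhere does not correct this sentence, and the protocol never states the charitable reading of risk.

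A reader might infer more than the documents support:

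- *That consent itself rests on a false statement, or is consent to a different study.* The consent form's text is not available, and the surgeon's discussion identifies the study correctly.
- *That the patient hears a conflicting account from the PA when signing.* Protection of Human Subjects does not say who makes the statement or when. The PA is to summarise the consent document, not this sentence.
- *That the use of rhBMP-2 here is necessarily off-label.* The Background gives an initial approval and mentions many off-label applications. It does not say that every other use is off-label.
- *That consent is the only safeguard, that the graft cannot be reversed, or that the standing of the data is in doubt.* The documents state none of these. The application is itself made to an IRB, and the eligibility criteria include safety exclusions.

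**Conclusion.** The point holds as an inconsistency in a statement intended for patients. The sentence misnames the arms, and its unqualified risk wording is not reconciled with the Background or with the surgeon's planned discussion. Patients could therefore receive a statement at odds with the rest of the protocol. Whether any would depends on whether the consent form or the verbal summary repeats it, which cannot be checked from these documents.

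The error is confined to wording and consent. Randomisation, endpoints, sample size and analysis do not depend on it. It should still be corrected, because the sentence governs what patients are told and the correction is easy. The conclusion assumes only that the sentence is meant to be followed as written.

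**What to change.** 1. Replace the reference to pain management groups with: *bone graft groups (Vivigen or rhBMP-2, each with local autograft)*.
2. Resolve the risk wording in one of two ways. Either state that each graft carries risks, including the rhBMP-2 adverse effects given in the Background and the limited evidence on cellular allograft. Or state explicitly that minimal risk refers only to the added risk of random allocation, and give the justification.
3. Check that the consent form and the PA's verbal summary do not repeat the present wording.
4. Do not add a statement that the graft cannot be reversed unless the sponsor confirms it.

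The cost is one revised sentence, a check of the consent form and an IRB notification. A few more patients may decline once the risks are stated plainly. Nothing in the design or analysis changes.
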